Over the past decade, however, there has been a growing body of literature suggesting that *Propionibacterium acnes* infection may play a significant role in a variety of pathological conditions affecting the native shoulder, most notably frozen shoulder^{4,5}. Our goal is to employ a treatment strategy focused on eradicating *P acnes* infection as a conservative treatment of adhesive capsulitis. **Through this proposal, we aim to complete a prospective randomized trial to examine the hypothesis that administration of intra-articular antibiotics effective against *P acnes* will prove to be a superior treatment of adhesive capsulitis as compared to current gold standard of intraarticular steroid injection.**

Specific Aim 1: Determine if intra-articular doxycycline is superior to intraarticular corticosteroid in the treatment of adhesive capsulitis.

We hypothesize that intra-articular doxycycline injection will be a more effective treatment of adhesive capsulitis than the current gold standard of intraarticular steroid injection. **Methods:** We will recruit a total of 40 patients from the Vanderbilt Sports Medicine Clinics who have been diagnosed with adhesive capsulitis and have not undergone any previous treatment. The 40 patients will be randomized, with 20 in the control group of 3 intra-articular injections of 40mg Methylprednisolone spaced every two weeks, and 20 in the experimental group of 3 intra-articular injection of 50mg doxycycline spaced every two weeks. Both groups will begin a standardized physical therapy program within a pain-free range of motion 4 weeks after the initiation of treatment. We will prospectively follow patients for one year, with follow-up at 6 weeks, 12 weeks, 6 months, and 12 months after the initiation of treatment. Outcomes will be measured using the American Shoulder and Elbow Score (ASES), which will be administered by the treating physician. Both the patients and physicians participating in the study will be blinded. **Anticipated Outcome:** We anticipate that patients treated with intra-articular doxycycline will have significantly higher ASES scores at each time point of follow-up as compared to patients treated with intra-articular corticosteroid injections.

The proposed study has the potential to make a significant and long-term impact on not only the treatment of adhesive capsulitis, but on the treatment of wide array of destructive joint disease. Over the past decade, there has been a growing body of literature suggesting a potential infectious etiology in an array of articular pathologies. Although classically thought to be the result of genetics and biomechanical forces, there is growing evidence that many pathological conditions, including osteoarthritis, degenerative disc disease, and adhesive capsulitis, may have an infectious origin⁴⁻⁶. In recent literature, *Propionibacterium acnes* has been identified as the potential infective pathogen underlying these conditions. This project could not only add significant evidence to support the role of *P acnes* in native joint dysfunction, but also introduce a potential novel treatment for these conditions, spurring new research opportunities across orthopaedic specialties.

Research Strategy

Significance: Adhesive capsulitis is a common condition of the shoulder joint affecting 2-5% of the adult population¹. For shoulder experts, sports medicine specialists, or general orthopaedists, adhesive capsulitis is a frequent diagnosis for which patients seek care. The condition often remains symptomatic for over a year despite treatment and results in significant morbidity and loss of function for those affected². Despite the significant number of patients affected by adhesive capsulitis and the extensive literature focused on the natural history and treatment of the condition, the true etiology remains poorly understood and no currently accepted treatment has proven to alter its natural history.

Over the past decade, however, there has been a growing body of literature suggesting that *Propionibacterium acnes* infection may play a significant role in a variety of pathological conditions of the shoulder^{4, 5}. *P acnes* is a gram-positive anaerobic bacillus that is closely associated with sebum-producing hair follicles and has been shown to preferentially colonize the shoulder and upper back⁷. Much of this literature has focused on the role of *P acnes* in post-operative infections, especially PJI after shoulder replacement and several authors have reported it to be the most common infecting organism after rotator cuff repair⁸⁻¹⁰. Recently and most significantly, however, there has been emerging evidence that *P acnes* may play a role in other conditions affecting the native shoulder, most notably osteoarthritis and adhesive capsulitis^{4, 5}. Levy et al found that joint fluid cultures were positive for *P acnes* in 23 of 55 patients undergoing primary shoulder joint replacement for osteoarthritis or cuff arthropathy and who did not have previous shoulder surgery of any kind⁵. Schneeberger et al reviewed 7 patients who initially presenting with diffuse, non-localized shoulder pain and were found to have undiagnosed low-grade infections at the time of surgery¹¹. None of these patients had ever undergone shoulder surgery. Of note, 3 of these 7 patients were had a pre-operative diagnosis of adhesive capsulitis and *P acnes* was found to be the infective organism in 5 of the 7 patients. Most relevant to the discussion of adhesive capsulitis, Bunker et al cultured synovial tissue from the shoulders of 10 consecutive patients with adhesive capsulitis undergoing arthroscopic release and found that 8 of the 10 patients had positive cultures, 6 of which grew *P acnes*⁴. This emerging research suggests that indolent *P acnes* infection could be the underlying cause of adhesive capsulitis.

To date, there have been no studies exploring whether empiric treatment of adhesive capsulitis with antibiotics effective against *P acnes* will lessen either the duration or severity of symptoms as compared to current treatment modalities. This project could not only add significant evidence to support the role of *P acnes* in adhesive capsulitis, but also introduce the first treatment modality that has potential to alter the natural history of the condition.

Materials and Methods: Patients meeting the inclusion criteria will be randomized into either the control group of 3 intra-articular injections of 40mg Methylprednisolone spaced every two weeks or the experimental group of 3 intra-articular injection of 50mg doxycycline spaced every two weeks, with 20 patients in each group. Female participants will have a urine pregnancy test done prior to the first injections. Injections will be administered by the treating physician. Both groups will begin a standardized physical therapy program within a pain-free range of motion 4 weeks after the initiation of treatment. Both the patients and physicians participating in the study will be blinded to the treatment received. The Vanderbilt Investigational Pharmacy will provide the doxycycline and the steroid solutions and will be in charge of patient randomization.

Doxycycline was selected as the experimental intervention for this study as it is effective against *P. acnes* and has been shown to be protective against joint damage in both *in vitro* and *in vivo* models¹²⁻¹⁶. Moreover, tetracyclines have been shown to be safe and effective for intra-articular use in the treatment of hemophilic arthropathy in humans and in multiple animal models¹⁷. The decision to use doxycycline 50mg was based on the general acceptance of using 50% of the standard systemic dose for intraarticular injections of antibiotics and the known stability of the antibiotic at a concentration of 10mg/ml¹⁸. This dosage will provide intraarticular levels of doxycycline well above the typical minimum inhibitory concentration (MIC) for doxycycline-susceptible *P. acnes*.

Data and Safety:

An independent physician ([name]) at VUMC will serve as the data safety monitor. The site will have monthly study meetings with the KSP to discuss number of eligible patients seen during the previous month, how many of them were approached for participation and how many of them consented or refused to participate. Protocol deviations and adverse events will be reviewed. The accumulative findings will be reported on an annual basis to the DSM.

All adverse events will be recorded and reported upon finding them. All serious adverse events will be reported to the Data Safety Monitor (DSM) within 48 hours of identification. The DSM will then review them with the PI within 72 hours and will notify the VUMC IRB Department within 10 business days.

Formal DSM reviews and reports will be conducted annually.

Data Collection: Patients will be followed prospectively for one year, with follow-up at 6 weeks, 12 weeks, 6 months, and 12 months after the initiation of treatment. Outcomes will be measured using the American Shoulder and Elbow Score (ASES), which will be administered by the treating physician at each follow-up visit. The ASES questionnaire was developed to provide a standardized method for evaluating shoulder function and has been validated in patients with any array of shoulder pathologies¹⁹⁻²³.

Data Analysis: ASES scores at each time point in follow-up will be input into SPSS software (SPSS Inc, Chicago, IL) for statistical analysis. Statistical tests for nonparametric variables will be used. Paired *t* tests will be used to compare paired groups for continuous variables. Independent *t* tests will be used to compare different treatment regimens. Level of significance will be set at *P* ≤ .05.

Potential Problems: Potential problems include possible allergic reactions to medications, or possibly introducing infection, which would be considered extremely rare. Patients enrolled will be carefully followed.

PROJECT TIMELINE

| 0-6 Months | 6-12 Months | 12-18 Months | 18-24 Months | 24-26 Months |
|--|--|---------------|------------------------|--------------|
| Patient enrollment, randomization, initiation of treatment | | | | |
| | Data collection at each follow-up time point | | | |
| | | Data analysis | | |
| | | | Manuscript preparation | |

HUMAN SUBJECTS

Description of Study:

We will recruit a total of 40 patients from the Vanderbilt Sports Medicine Clinics who have been diagnosed with adhesive capsulitis and have not undergone any previous treatment. The 40 patients will be randomized, with 20 in the control group of 3 intra-articular injections of 40mg Methylprednisolone spaced every two weeks, and 20 in the experimental group of 3 intra-articular injection of 50mg doxycycline spaced every two weeks. Both groups will begin a standardized physical therapy program within a pain-free range of motion 4 weeks after the initiation of treatment. Both groups will begin a standardized physical therapy program within a pain-free range of motion 4 weeks after the initiation of treatment. We will prospectively follow patients for one year, with follow-up at 6 weeks, 12 weeks, 6 months, and 12 months after the initiation of treatment. Outcomes will be measured using the American Shoulder and Elbow Score (ASES), which will be administered by the treating physician. Both the patients and physicians participating in the study will be blinded.

Potential risks and complications:

Because patient data is being collected there is a slight risk of a breach of confidentiality. To reduce this risk, most study data will be maintained in a Vanderbilt REDCap database. Vanderbilt Redcap is a secure, web-based application for building and managing online databases and surveys. The data obtained and stored in Redcap will only be accessible by research personnel. All study data will be maintained for 6 years following study completion. Following this 6 year period, the Redcap database will be archived and all physical study forms will be disposed of in shred-it confidentiality bins provided by VUMC.

The drugs used in this study are not narcotics or habit-forming but can have side effects. The treating physician will screen for any condition that would increase the chance for the patient to have an unwanted side effect. However, there is a small possibility that an injection of these medicines can be painful and cause bleeding or infection.

Statement of confidentiality:

During this study, every attempt will be made to keep the patient's protected health information (PHI) private. Most study data will be maintained in a Vanderbilt REDCap database. Vanderbilt Redcap is a secure, web-based application for building and managing online databases and surveys. The data obtained and stored in Redcap will only be accessible by research personnel. Any data sent to non-key study personnel for statistical analysis will be de-identified (dates will be shifted using a Redcap feature). Any physical study forms (ex. consent documents, surveys) will be kept in a locked cabinet in the Vanderbilt Orthopaedic Institute Administrative Offices. All study data will be maintained for 6 years following study completion.

Following this 6 year period, the Redcap database will be archived and all physical study forms will be disposed of in shred-it confidentiality bins provided by VUMC.

Allowance for non-prejudicial withdrawal for investigation:

Participation in this study is completely voluntary. If the study participant wishes to be withdrawn from the prospective portion of this study following consent, they may do so by letting the key study personnel know they withdraw their consent. All data collected up to the point of the patient's study withdrawal will be included in study analysis.

Liability and hold harmless clause:

If it is determined by Vanderbilt and the Investigator that an injury occurred as a direct result of the tests or treatments that are done for research, then the patients and/or their insurance will not have to pay for the cost of immediate medical care provided at Vanderbilt to treat the injury.

There are no plans for Vanderbilt to pay for the costs of any additional care. There are no plans for Vanderbilt to give the patient money for the injury.

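### The plan states no visit at which adverse events are asked about and no adverse event result by arm, so short-lived injection reactions are liable to be under-counted

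*Combined protocol and SAP*

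**What the plan says.** **Capture.** The rule in Data and Safety is "All adverse events will be recorded and reported upon finding them". For serious events the section adds "All serious adverse events will be reported to the Data Safety Monitor (DSM) within 48 hours of identification", followed by deadlines for the monitor's review and for notifying the IRB.

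**Oversight.** An independent physician acts as safety monitor. In connection with the monthly study meetings the section says "Protocol deviations and adverse events will be reviewed", and then "The accumulative findings will be reported on an annual basis to the DSM". Neither is said to be by arm.

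**Follow-up visits.** Data Collection lists one measure: "Outcomes will be measured using the American Shoulder and Elbow Score (ASES), which will be administered by the treating physician at each follow-up visit".

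**Analysis.** Data Analysis begins "ASES scores at each time point in follow-up will be input into SPSS software" and names no other variable. For the comparison of arms it says "Independent *t* tests will be used to compare different treatment regimens".

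**Named harms.** Potential Problems names allergic reaction and introduced infection, which it expects to be very rare. Potential risks and complications says "there is a small possibility that an injection of these medicines can be painful and cause bleeding or infection". Together these make four: allergic reaction, pain, bleeding and infection. None is tied to a collection step or to an analysis.

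**The concern.** The trial would put three intra-articular doxycycline injections forward as superior to steroid on a shoulder-function score. The background section says that no study has yet explored empiric antibiotic treatment of this condition. The safety support in Materials and Methods comes from tetracyclines used in hemophilic arthropathy and in animal models. Tolerability in this population is therefore something readers will expect the trial to report.

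A pain flare or a mild skin reaction can come and go between two visits. If nobody asks, it enters the data only when the patient mentions it or someone notices it. With 20 patients per arm, the recorded counts may then say little about either drug. Reactions that were never asked about cannot be recovered reliably later.

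**Working it through.** The plan states no adverse event rate, capture rate or safety precision, so there is no figure of its own to reproduce.

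**1. Timing.** Three injections two weeks apart fall at weeks 0, 2 and 4 (Materials and Methods). The first follow-up is at week 6 (Data Collection). There are 20 × 3 = 60 planned injections per arm and 120 in all. Contacts during treatment are at weeks 0, 2, 4 and 6, so the longest gap in that period is two weeks. A reaction lasting a few days can fall wholly inside such a gap.

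**2. Is there a question at any of these contacts?** Set side by side:

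| Provision | What it governs | Does it seek out events? |
|---|---|---|
| Recording when found | Prompt recording | Not stated |
| Monthly review | Events already on record | No |
| Annual report to the monitor | Cumulative findings | No |
| 48-hour rule | Clock that starts at identification | No |
| Follow-up visits | ASES | Not stated |
| Injection visits | Giving the injection | Not stated |

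No collection window or grading scale is given either.

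**3. What incomplete capture could do.** The true rates and capture fractions below are assumptions; the document gives none. If a harm has true rate p and a fraction c of cases is recorded, the chance that at least one case is recorded among 20 patients is 1 − (1 − pc)^20.

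| True rate p | c = 100% | c = 50% | c = 25% |
|---|---|---|---|
| 5% | 1 − 0.95^20 = 64% | 1 − 0.975^20 = 40% | 1 − 0.9875^20 = 22% |
| 10% | 1 − 0.90^20 = 88% | 1 − 0.95^20 = 64% | 1 − 0.975^20 = 40% |

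Incomplete capture also shrinks a difference between arms, even when it is equal in both. Suppose injection pain truly affects 30% of one arm and 10% of the other (assumed). The expected counts are 20 × 0.30 = 6 and 20 × 0.10 = 2 with full capture. With half capture they are 3 and 1. Approximate power for that difference falls from 35% to 18%.

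**4. What 20 per arm can support with full capture.** For 0 of 20, the two-sided Clopper-Pearson upper 95% limit is 1 − 0.025^(1/20) = 16.8%. Fisher's exact test of x/20 against 0/20 gives p = 0.106 at x = 4 and p = 0.047 at x = 5. Even with full capture, 5% against 20% has only about 30% power. These limits come from the sample size, not from the capture method. They are the reason the result by arm should be descriptive.

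**The case against.** The strongest reply is that the recording sentence sets when events are reported, not how they are sought. Read with the 48-hour rule that follows it, that is a fair reading. A reader might infer that the plan has chosen passive reporting, or that no visit includes a safety question. The document supports neither. It is silent on elicitation, visit procedures are not itemised, and the Appendix 1 form and the consent pages are not available. What can be said is that no such question is stated.

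It can also be said that there is a safety system: an independent monitor, monthly review, annual reports, deadlines for serious events, and an assurance in Potential Problems that patients will be followed carefully. That stands and deserves credit. But these provisions oversee events once found, and the assurance is not a method.

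A reader might take the week-6 follow-up to be the first look at a patient after treatment. It is not. The treating physician gives every injection and so sees the patient at weeks 2 and 4 as well. Those visits are chances to notice an event; the gap is that no query is specified at them.

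Finally, a reader might infer that events will never be compared. That too goes beyond the text. All events are to be recorded and arm is known from randomization, so a table could be made. What is absent is a plan to present one.

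**Conclusion.** The point holds in a limited form. The plan states no systematic way of asking about adverse events and plans no adverse event result by arm beside the ASES comparison. The named injection harms are liable to be under-counted.

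It would be too strong to say that they are under-counted, or that most reactions would go unrecorded. The size depends on event rates and capture fractions that the document does not give, and the figures in the working only illustrate assumed values. Nor does the 16.8% limit measure the capture problem. It would apply with perfect capture and shows only how little 20 patients can exclude.

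This is a worthwhile, inexpensive improvement and does not affect the efficacy analysis. The form matters more than the table. A table can be added at reporting, whereas answers not sought at the visits cannot be recovered. The change should therefore be made before enrolment.

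**What to change.** 1. **Data and Safety.** Keep the rule that any event is recorded promptly when found. Add one short solicited form, identical in both arms, before injections 2 and 3 and at the week-6, week-12, month-6 and month-12 visits. It asks about pain flare after injection, bleeding, signs of infection, allergic or skin reaction, and anything else, with onset date. The patient completes it, and the blinded treating physician grades severity on a scale named in the protocol. Each form covers the time since the previous contact. The form must supplement unsolicited reporting, not replace it, because later visits are up to six months apart.

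2. **Data Analysis.** Add a table of the number and proportion of participants with each event, by arm, with exact 95% confidence intervals, reported beside the ASES result. State that it is descriptive and that no hypothesis test will be done.

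**Cost.** One form in the REDCap database already planned, a few minutes at each of six existing visits, and one table. There are no new visits and no change to sample size or significance level. Recorded adverse event counts will be higher than without the form, and the report should say that events were solicited.

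### ASES, the only named efficacy outcome, is administered by the same role that injects, so its collection depends without need on a physician blind whose method is not described

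*Combined protocol and SAP*

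**What the plan says.** - **Outcome.** ASES is the only efficacy outcome named. Under Data Collection: "ASES), which will be administered by the treating physician at each follow-up visit". Specific Aim 1 and Description of Study give the task to the same role and add the blinding statement: "which will be administered by the treating physician. Both the patients and physicians participating in the study will be blinded".
- **Injections.** Materials and Methods: "Injections will be administered by the treating physician".
- **Blinding.** Materials and Methods: "Both the patients and physicians participating in the study will be blinded to the treatment received". On supply and allocation: "The Vanderbilt Investigational Pharmacy will provide the doxycycline and the steroid solutions and will be in charge of patient randomization". No section describes how the two products are made indistinguishable, names a separate assessor, or plans a check of the blind.
- **Type of instrument.** Data Collection: "The ASES questionnaire was developed to provide a standardized method for evaluating shoulder function". The title of Appendix 1 identifies the form as the patient evaluation part of ASES. Only that title is available in the text reviewed.
- **Expected direction.** Specific Aim 1: "We anticipate that patients treated with intra-articular doxycycline will have significantly higher ASES scores at each time point of follow-up".

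**The concern.** The treating-physician role handles the product at injection and later collects the only efficacy outcome. If an assessing physician has seen or guessed which drug was given, the way questions are put, explained or scored could differ by arm. The planned independent t tests could not tell such a shift from a drug effect, and no later analysis could separate them. The study hypothesis favours doxycycline at every visit, so a shift in that direction is plausible. Individual physicians' expectations are not documented, so the direction is not known.

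The plan accepts this exposure without need. A form meant for the patient's own evaluation can be filled in before the physician enters the room.

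**Working it through.** **Who does what**

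| Task | Role | Where |
|---|---|---|
| Supplies products, randomises | Investigational pharmacy | Materials and Methods |
| Injects | Treating physician | Materials and Methods |
| Administers ASES | Treating physician | Specific Aim 1, Data Collection, Description of Study |
| Stated to be blinded | Patients and physicians | Specific Aim 1, Materials and Methods, Description of Study |

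Volume of contact: 40 patients × 3 injections = 120 injections, and 40 × 4 visits = 160 ASES assessments, all assigned to one role.

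**Timing.** Three injections two weeks apart, counting the first as week 0, fall at weeks 0, 2 and 4. The listed ASES visits are at 6 weeks, 12 weeks, 6 months and 12 months, so none coincides with an injection. Any influence at a visit would have to come from something seen or guessed earlier.

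**Illustrative size.** The plan has no figure to reproduce here: it gives no ASES SD and no estimate of assessor bias.

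Inputs from the documents: 20 per arm, independent t test, significance level 0.05. Sidedness is not stated; two-sided is assumed. The average shift in favour of doxycycline, b (in SD units), is also assumed.

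- Degrees of freedom: 20 + 20 − 2 = 38. Critical t = 2.024.
- Critical difference: 2.024 × √(2/20) = 0.640 SD.
- Noncentrality with no true effect and shift b: b / √(2/20) = b × √10.

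| Assumed b (SD) | Noncentrality | False doxycycline win | False steroid win | Two-sided false positive |
|---|---|---|---|---|
| 0 | 0 | 0.0250 | 0.0250 | 0.0500 |
| 0.05 | 0.158 | 0.0355 | 0.0173 | 0.0527 |
| 0.1 | 0.316 | 0.0493 | 0.0117 | 0.0610 |
| 0.2 | 0.632 | 0.0896 | 0.0050 | 0.0946 |

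Totals are taken before rounding. The rates are for one visit. The two smaller shifts change little. The 0.2 SD shift nearly doubles the false-positive rate, but it is an average over all patients: if the arm were guessed correctly in half of them and the rest were unaffected, it would take 0.2 / 0.5 = 0.4 SD in those guessed.

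**The case against.** The strongest reply is that physicians are blinded. The plan says so in three places and puts supply and randomisation with a pharmacy outside the clinic. One role both treating and assessing is no contradiction when that role is blinded. This stands: if the blind holds, the bias is zero.

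A second reply is that the plan may already intend self-completion. The instrument is called a questionnaire, its title points to the patient, and the Statement of confidentiality counts surveys among the physical study forms. Administering may mean no more than handing over the form. This also stands as a possible reading, and the change is then a clarification. The current wording equally allows reading aloud or scoring by the physician.

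A third reply is that self-completion does not address the real gap, which is the undescribed masking: a cue visible to the injector may be visible to the patient too. That is a fair limit on the remedy. A physician who guessed the arm could also convey expectations at an injection or at an earlier follow-up visit.

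Three stronger readings are tempting but not supported:

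- *The blind is broken.* No section shows this. A missing description of masking is not evidence that masking fails.
- *The injected volume reveals the arm.* Materials and Methods mentions the "known stability of the antibiotic at a concentration of 10mg/ml". At that concentration 50 mg would occupy 50 / 10 = 5 ml. But the figure is given as part of the reasoning for the dose, not as the injected volume, and no steroid volume is stated, so no visible difference can be inferred.
- *The same individual injects and assesses each patient.* The text names a role. One person doing both is a natural reading, but it is not stated.

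**Conclusion.** The concern holds as an avoidable dependence, not as a demonstrated bias. The only named efficacy outcome is collected by the role that injects, under a blind that is asserted without a described method, although the form appears to be one that patients can complete themselves.

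The size is unknown and is zero if the blind holds. The rates of 5.3%, 6.1% and 9.5% rest on assumed shifts of 0.05, 0.1 and 0.2 SD, a two-sided test and no true effect. They show what such shifts would do and do not estimate what will happen in this trial. Priority is optional to moderate: the case for acting rests on the low cost of the change, not on evidence of harm.

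**What to change.** - **Specific Aim 1 and Description of Study.** Replace the phrase giving ASES administration to the treating physician with: *completed by the patient before seeing the treating physician at each follow-up visit*.
- **Data Collection.** Make the same replacement, covering the whole phrase including its reference to follow-up visits, so that those words are not repeated.
- **Completeness.** Add that study personnel other than the treating physician check the form for skipped items.

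**What it achieves.** It removes the physician's influence on how answers are elicited and scored at that visit. It does not remove expectations conveyed earlier, and it does not protect against a patient who learns the arm.

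**Cost.** One phrase in three places, with no extra assessor and no change in sample size. Paper would suffice; REDCap, already the study database and described as supporting surveys, is an alternative. The downsides are some skipped items and a short check at each visit. The documents do not assign anyone other than the treating physician to the follow-up visits, so the sponsor should confirm who will do the check.

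**Separate clarification, not part of this fix.** One sentence in Materials and Methods could state how the pharmacy masks the two products and whether any difference is visible to injector or patient. It requires no change to dose or preparation.

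### Per-visit t tests with no missing-data method give no weight to the retained early scores of patients who leave, so later ASES comparisons are at risk if dropout is outcome-related and differs by arm

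*Combined protocol and SAP*

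**What the plan says.** Three places in the combined protocol and SAP bear on this.

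- Human Subjects, paragraph on non-prejudicial withdrawal: everything recorded up to a patient's "study withdrawal will be included in study analysis". Nothing is said about visits after that point.
- Approach, Data Analysis: "ASES scores at each time point in follow-up will be input into SPSS software"; between arms, independent t "tests will be used to compare different treatment regimens"; within arms, paired t "tests will be used to compare paired groups for continuous variables". Tests for nonparametric variables are mentioned but not named.
- Specific Aim 1, Anticipated Outcome: the doxycycline arm is expected to show "significantly higher ASES scores at each time point of follow-up as compared to patients treated with intra-articular corticosteroid injections".

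Data Collection sets "follow-up at 6 weeks, 12 weeks, 6 months, and 12 months after the initiation of treatment", and Materials and Methods randomises "with 20 patients in each group". The documents contain no repeated-measures model, imputation rule, analysis population, dropout allowance or sensitivity analysis. No visit is named as primary.

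**The concern.** A t test at a visit uses only patients who have a score at that visit. A paired t test needs both scores of its pair, and a rank test in place of the t test has the same limit. With no imputation or longitudinal model named, a patient who leaves drops out of every later comparison, and the scores already on file have no influence on the later estimates. The same applies to a missed visit without withdrawal.

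Follow-up lasts a year in a painful condition that eventually resolves. Both recovered patients and poor responders may stop attending, and the mix could differ between arms. If it does, the 6- and 12-month differences, which matter most for a claim about altering the course of the condition, compare groups that are no longer balanced by randomisation. With 20 per arm, each lost patient is 1/20 = 5% of an arm.

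**Working it through.** **1. Inputs.** From the documents: 20 per arm, four follow-up visits, independent t tests, significance level 0.05 (two-sided assumed). Not given: SD, effect size, between-visit correlation, dropout rate. There is no figure in the plan to reproduce, so everything below is illustration under stated assumptions.

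**2. Who is counted.** For a patient who leaves after the 12-week visit:

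| Visit | Score on file | Used in that visit's t test | Earlier scores used |
|---|---|---|---|
| 6 weeks | yes | yes | – |
| 12 weeks | yes | yes | no |
| 6 months | no | no | no |
| 12 months | no | no | no |

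**3. When this biases the difference.** Suppose leaving depends on the 12-week score, whose correlation with the 12-month score is ρ. Let s be the mean 12-week score of those who stay minus that of all randomised in the arm, in SD units. With no true effect,

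bias = ρ × SD × (s for doxycycline − s for control).

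Equal shifts cancel. Bias needs dropout that is related to outcome and that differs by arm.

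**4. Size.** Assumed: true 12-month difference 0, ρ = 0.5 or 0.7, departure after 12 weeks with odds depending on the 12-week score, 4,000 simulated trials per row. Points are SD units × an assumed SD of 20. Paired entries are for ρ = 0.5 and 0.7.

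| Who leaves (control / doxycycline loss) | t-test bias, SD | Points | False-positive rate | Likelihood-estimate bias, SD |
|---|---|---|---|---|
| Poor responders, both arms (20% / 20%) | −0.004; −0.006 | −0.1; −0.1 | 4.4%; 5.4% | −0.005; −0.006 |
| Poor responders, both arms (10% / 30%) | 0.095; 0.133 | 1.9; 2.7 | 6.0%; 6.4% | 0.001; −0.001 |
| Recovered controls, poor doxycycline responders (20% / 20%) | 0.187; 0.262 | 3.7; 5.2 | 8.4%; 12.0% | 0.001; 0.001 |
| Same opposite pattern (30% / 30%) | 0.280; 0.384 | 5.6; 7.7 | 11.4%; 18.6% | −0.004; −0.012 |

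The results follow the formula. Dividing bias by ρ gives the same net shift at both correlations: 0.095/0.5 = 0.19 and 0.133/0.7 = 0.19; 0.280/0.5 = 0.56 and 0.384/0.7 = 0.55. Further runs of the opposite pattern at about 25% loss gave 5.0–7.8 points and false-positive rates of 11–19%.

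**5. Against the noise.** With 10% and 30% loss, 18 and 14 patients remain. The standard error is 20 × √(1/18 + 1/14) = 7.1 points, so a bias of 1.9–2.7 points is 0.27–0.38 standard errors. That is why the false-positive rate moves little in that row.

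**6. Limits of the alternative.** The near-zero last column holds because dropout was made to depend only on an observed score (missing at random). When the opposite pattern was driven by the unseen 12-month score instead, the t test was biased by about 8.4 points and the likelihood estimate by about 4.6–6.5 points: better, not unbiased. When dropout is unrelated to outcome, both are unbiased and the likelihood standard error is about 3–6% smaller. No false-positive rate was computed for the likelihood model.

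**The case against.** A reader might infer that the withdrawal paragraph and the analysis paragraph contradict each other. They do not. Scores taken before withdrawal still enter the comparisons at the visits where they were taken. The sentence also reads as a rule on keeping data after consent is withdrawn, not as a promise that early scores will inform later estimates. Nor does the plan say that missing scores are excluded; that follows from the tests it names and from its silence on any other handling. This part of the objection stands.

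A reader might also infer that the t tests are unbiased only if leaving is unrelated to earlier scores. That is too strong: the first row of the table shows no bias under no true effect when rate and mechanism match in both arms.

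The objection is also right that the largest figures need opposite selection in the two arms. Nothing in the documents points to that, and patients and physicians are to be blinded. SD, correlation and dropout rates are all assumed.

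What does not stand is the view that only a missing policy remains. The plan names an analysis method, and applied as written that method determines who is counted at each visit. Another method makes better use of data the trial already intends to collect.

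**Conclusion.** The point holds as an avoidable weakness in the between-arm analysis, not as an inconsistency in the plan. As written, each later comparison is an available-case analysis that ignores the earlier scores of patients who left. Under the assumptions above (SD 20, correlation 0.5 to 0.7, roughly 20–25% dropout, no true effect), the risk is about 2–3 ASES points with unequal dropout rates, with a false-positive rate of about 5–7%. In an extreme opposite-direction pattern it is about 5–8 points, with a rate of about 11–20%. If rate and mechanism are the same in both arms, there is no bias under no true effect. The actual size cannot be computed from the documents.

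A reader might take the near-zero bias of the likelihood estimate as a guarantee. It is not one: it rests on missing at random.

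**What to change.** Make the between-arm analysis one likelihood-based repeated-measures model:

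- all randomised patients in their assigned arm, with every observed ASES score at 6 weeks, 12 weeks, 6 months and 12 months;
- terms for arm, visit and arm-by-visit, plus baseline ASES if it is recorded (Data Collection lists follow-up visits only);
- unstructured covariance, with a simpler structure named in advance in case it does not converge with 40 patients;
- Kenward-Roger small-sample correction.

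Report the arm difference at each planned visit from this model, or at one visit if the sponsor names a primary one before unblinding. Keep the per-visit t tests as a secondary analysis. Add a delta-adjusted sensitivity analysis for not-at-random dropout, and report withdrawals with reasons by arm.

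Cost: a revised analysis paragraph and slightly more programming, with no extra patients, visits or data. The downside is reliance on missing at random, which reduces but does not remove bias if dropout depends on unseen scores; the sensitivity analysis is there for that reason. Multiple imputation on all randomised patients would be a reasonable alternative.
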